4. SYNOPSIS

Study title	InterFast
Study design	Cohort study with an embedded randomized controlled pilot trial
Study participants	Healthy subjects and subjects who do already practice Alternate Day Fasting
Number of participants	90 (30 Participants in Alternate Day Fasting group and 60 participants in the control group). Those participants in the control group will be asked to participate in a short randomized controlled trial, where they will be either allocated to an Alternative Day Fasting group or another control visit.
Planned duration	18 months
Primary objective	The primary objective is to elucidate in which extent alternate day fasting influences human physiology in healthy individuals in both, the short and long term. Data of the pilot RCT will help to design a larger trial investigating Alternate Day Fasting in various groups of interest.
Secondary objectives	The secondary objective of this study is to define novel molecular markers of aging and age-related diseases.

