10. SELECTION AND WITHDRAWAL OF STUDY SUBJECTS

10.1 Subject Selection

The study population will consist of 100 healthy subjects. Fifty participants of them should already practice Alternate Day Fasting. Subjects in the ADF and control group will at least be matched by sex, weight and age. Subjects of the control group will be asked to participate in a pilot randomized controlled trial. A separate informed consent will be used for the intervention study.

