12.26 Data analysis and sample size estimation

Data analysis

Statistical Analyses for primary and secondary outcomes as well as for baseline values are done in a descriptive and exploratory way.

Continuous variables will be summarized with standard descriptive statistics tables and represented graphically with displays such as box plots and histograms, and categorical variables will be described by frequency tables and standard graphical displays like bar plots. Scatterplots are used to illustrate possible correlations between the variables.

To examine differences between groups at baseline and following visits, Student's T-tests or Mann-Whitney U tests and chi-square tests will be used as appropriate. Comparisons within groups will be performed using paired T-test or Wilcoxon rank-sum test. A p-value of <0.05 is considered to indicate statistical significance, whereas appropriate correction for multiple testing like Bonferroni Correction or false discovery rate (*Benjamini and Hochberg*) will be applied. To investigate multiple relations generalized linear mixed models will be built to investigate changes between groups and over time, as the physiological changes are represented in various parameters. For high-dimensional "omics-" data appropriate multivariate modelling like Random Forests and Partial Least Squares Regression will be used to elucidate differences between groups and time-points concerning potential molecular markers regarding aging effects.

A statistical analysis plan will be prepared and finalized before database lock. All statistical analysis will be done in R (version 3.0.1.).

Sample size estimation

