Data on the effects of ADF on metabolic parameters, human physiology, aging process and molecular cellular processes in healthy subjects is very limited and a therefore an accurate sample size estimation impossible. However, we reviewed available data and used data on insulin sensitivity from a similar, albeit not entirely comparable study population with a HOMA-IR of 3 ± 1.1 (mean \pm SD)⁷. Assuming a power of 80% and a type I error rate of 5%, we would need 50 subjects per group to demonstrate an effect size of 15%, which has been demonstrated previously³⁸. Therefore the sample size of 50 subjects in the ADF and 50 subjects in the control group, as chosen for our cohort study, seems to be reasonable. In addition, previous publications have also suggested a sample size of 50 subjects per group for such types of studies with insufficient details about the outcome parameters required for a sample size estimation³⁹. Subjects in the control group will be asked to participate in a pilot, randomized controlled trial, where they are randomized to either ADF or continuing in the control group. We expect an acceptance rate of about 40%, hence a sample size of about 10 participants per group.

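### The sample size does not follow from its inputs: 50 per group gives about 53% power for a 15% HOMA-IR difference, not 80%, and the planned 30/60 split gives about 44%

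*Protocol*

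**What the plan says.** The sample size part of Protocol section 12.26 starts from a "study population with a HOMA-IR of 3 ± 1.1" (mean and SD), taken from a population that the protocol itself calls not entirely comparable. It continues: "Assuming a power of 80% and a type I error rate of 5" per cent, "we would need 50 subjects per group to demonstrate an effect size of 15" per cent. From this it concludes that 50 fasting participants and 50 controls are reasonable, and it adds as further support a publication that suggests 50 per group when details for a calculation are lacking. For the embedded pilot trial it says: "We expect an acceptance rate of about 40%, hence a sample size of about 10 participants per group".

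The current text gives two different cohort sizes:

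- Section 4 (Synopsis): "90 (30 Participants in Alternate Day Fasting group and 60 participants in the control group"). The amendment history (section 3, amendment 6) records the fall in the total from 100 to 90.
- Section 10.1: "The study population will consist of 100 healthy subjects. Fifty participants of them should already practice Alternate Day Fasting". Section 12.26 uses the same 50 and 50.

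The data analysis part of section 12.26 assigns unpaired tests (t-test or Mann-Whitney) to comparisons between groups and paired tests to comparisons within groups. It sets significance at p<0.05 and says that "appropriate correction for multiple testing like Bonferroni Correction or false discovery rate" will be applied.

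**The concern.** A 15% difference on a mean of 3 is 0.45, which is about 0.41 of the stated SD. A standardised difference of that size needs close to 100 per group in a two-group comparison, so 50 looked too small by a factor of about two. That is the factor that separates the two-sample formula from the one-sample or paired formula.

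The calculation was also not redone when the total fell to 90 and the allocation became unequal, which lowers power further.

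Insulin sensitivity is a primary outcome of the cohort (section 8.1) and HOMA is one of its named measures. A reader who accepts 80% power could take a non-significant HOMA-IR result as evidence against a 15% effect. At 30/60, two-sided, the chance of missing such an effect is 1 − 0.44 = 56%. The figures would also mislead anyone who uses this study to plan the larger trial that the synopsis mentions.

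**Working it through.** **Inputs (section 12.26 unless noted)**

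- Mean 3, SD 1.1. The SD is read as a between-subject SD.
- Effect 15%, read as 0.15 × 3 = 0.45 HOMA-IR units, so d = 0.45/1.1 = 0.409.
- Power 80%, type I error 5%. Sidedness is not stated, so both are shown.
- Allocation 50/50 (sections 10.1 and 12.26) or 30/60 (section 4).
- No allowance for dropout is stated.

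**Step 1. Trying to reproduce 50 per group**

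Two-sample formula, two-sided: n = 2(1.960 + 0.842)²/d² = 93.8, so 94 per group; 95 with the noncentral t.

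Two-sample formula, one-sided: n = 2(1.645 + 0.842)²/d² = 73.9, so 74 per group; 75 with the noncentral t.

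One-sample or paired formula, two-sided: n = (1.960 + 0.842)²/d² = 46.9; 49 with the t distribution. This is the only reading tried that matches the stated 50 without adding an input the protocol does not give.

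Other two-group readings, per group (normal approximation):

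| Reading | Two-sided | One-sided |
|---|---|---|
| Log scale, CV 1.1/3 = 0.367, ratio 0.85 | 75 | 60 |
| Log scale, CV 0.367, ratio 1.15 | 102 | 80 |
| SD proportional to the mean | 81 | 64 |
| 15% reduction from 3.53 to 3 | 68 | 54 |

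The closest, 54, needs both a one-sided test and the most favourable reading of 15%. Even then, power at 50/50 is about 78%.

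**Step 2. Power for a difference of 0.45, SD 1.1 (noncentral t)**

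| Allocation | Two-sided 5% | One-sided 5% |
|---|---|---|
| 50/50 | 52.6% | 65.0% |
| 30/60 | 44.0% | 56.8% |

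A simulation of 50,000 trials gave 52.5% and 44.2% for the two-sided column.

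**Step 3. Difference detectable with 80% power (two-sided t-test)**

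- 50/50: d = 0.566; 0.566 × 1.1 = 0.62; 0.62/3 = 20.7%.
- 30/60: d = 0.633; 0.633 × 1.1 = 0.70; 0.70/3 = 23.2%.

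For 50 per group to be right for 0.45, the SD would have to be 0.45/0.566 = 0.80, not 1.1. A 1:2 split with 80% power for 0.45 would need about 71 and 142.

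**Step 4. Sensitivity to the SD**

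The source population differs from this one, so the coefficient of variation is uncertain. If it lay anywhere from 0.30 to 0.50 (an assumed range), two-sided power for 15% at 30/60 would run from 60% down to 26%.

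**Step 5. Pilot trial**

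The stated 10 per group is 0.40 × 50/2 = 10, which uses the old control group. With 60 controls it is 0.40 × 60/2 = 12.

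**Step 6. Multiplicity, as illustration only**

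The calculation uses an unadjusted 5%. Section 8.1 lists seven primary outcome domains. If Bonferroni were applied across seven (0.05/7 = 0.0071), power for 0.45 would be 25% at 50/50 and 18% at 30/60. The protocol fixes neither the method nor the family, so these figures are not part of the error.

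**The case against.** The strongest defence is that the protocol claims little for this calculation. It says an accurate estimate is impossible, that the source population is not entirely comparable, and that all analyses are descriptive and exploratory. No confirmatory decision rests on HOMA-IR, which is one of four insulin sensitivity indices within one of seven primary domains. All of this stands and reduces the consequence. It concerns the uncertainty of the inputs, however, not the arithmetic done on them, and section 12.26 then uses the result to call the size reasonable.

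A second defence is that the cited publication supports 50 per group independently. It does not support the current plan, because a fasting group of 30 does not meet that rule.

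A third is that the groups are matched by sex, weight and age (section 10.1), so a paired formula might have been meant. But the between-group tests are unpaired, and 50 is given per group. Using SD 1.1 for pair differences would imply a within-pair correlation of 0.5, which the protocol does not give, and 30 against 60 cannot form 50 pairs. Covariate adjustment with a correlation near 0.7 would bring the requirement to about 48 per group, but no such correlation or adjusted analysis is stated as the basis for the sample size.

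Some limits on the criticism are fair:

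- A chance above one half of missing a 15% effect holds only for 30/60, two-sided. It is 47% at 50/50 two-sided, and 43% at 30/60 one-sided.
- Ten against 12 per arm is a small gap for a pilot described with "about" and no power claim. The 40% acceptance rate was also written for the old design.
- The 30/60 split is the plan in the synopsis; the amendment history records only the total.

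**Conclusion.** The concern holds. The stated inputs give 95 per group two-sided (75 one-sided), not 50. Two-sided power for a 15% HOMA-IR difference is 52.6% at 50/50 and 44.0% at the 30/60 split in the synopsis; one-sided it is 65.0% and 56.8%. The 80% claim fails on every two-group reading tried. These figures assume that 15% means 0.45 units on the raw scale and that SD 1.1 is the between-subject SD in both groups.

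Separately, and without any assumption, sections 10.1 and 12.26 contradict the synopsis on both the total and the allocation. Both faults are in current protocol text and need correction. The multiplicity figures and the pilot-trial size are secondary.

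**What to change.** Keep the 90 participants and correct the text:

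- **Section 12.26, cohort.** Delete the statement that 50 per group are needed for a 15% effect, and the conclusion and rule-of-thumb support tied to 50 per group. State instead that with 30 fasting participants and 60 controls, SD 1.1 and a two-sided 5% t-test, the cohort has 80% power for a HOMA-IR difference of about 0.70 (23% of 3) and about 44% power for 15%. State the sidedness and the scale of the percentage, and say that no multiplicity correction or dropout allowance is included. Retain the caveat about the source population.
- **Section 10.1.** Change 100 and 50 to 90, with 30 fasting participants and 60 controls, after the team confirms that the synopsis is the intended design.
- **Section 12.26, pilot trial.** Change the expectation to about 24 participants (12 per arm) if the team still expects 40% acceptance.

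The cost is a rewording of two sections and a less favourable stated power or detectable difference. No extra participants or procedures are needed.

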12.27 Markers of cardiovascular risk

Serum Aliquots of 40 subjects will be used for miRNA-analyses (atherosclerosis-related intracellular signals) regarding cardiovascular risk between Japanese and Austrian cohorts (in cooperation with [name] PhD; Hyogo College of Medicine; Japan).

13. STUDY MONITORING

A risk-based approach will be taken to determine the frequency of study monitoring for the study which will be agreed with the Principal Investigator. Monitoring will be undertaken according to ICH GCP and the study monitoring plan. The study monitor will be suitably trained, qualified and experienced to

perform this task. Data will be evaluated for compliance with the protocol and accuracy in relation to source documents.

14. ETHICS

The Investigator will ensure that this study is conducted in accordance with the principles of the Declaration of Helsinki, GCP-ICH and according to the protocol and the requirements of the concerned regulatory authorities. The measurements taken are either non-invasive or minimally invasive (blood sampling). Therefore we consider this trial as low risk for participants.

14.1 Informed Consent

- 1. Informed consent will be obtained for all participants in the study by the study physician.
- 2. Written versions of the subject information and Informed consent will be presented to the subjects detailing:
 - The exact nature of the study
 - The implications and constraints of the protocol
 - The known side effects and any risks involved in taking part.
- 3. It will be clearly stated that the subject is free to discontinue their participation in the study at any time for any reason without prejudice to future care, and with no obligation to give the reason for withdrawal.
- 4. The subject will be allowed as much time as wished to consider the information, and the opportunity to question the Investigator, their usual care provider or other independent parties to decide whether they will participate in the study. Written Informed Consent will then be obtained by means of subject dated signature and dated signature of the person who presented and obtained the informed consent.
- 5. A copy of the signed Informed Consent will be given to the subjects. The original signed form will be retained at the study site.
-
- Every subjects participating in the cohort study will need to sign the cohort study informed consent and in addition the biobank informed consent. Those subjects willing to participate in the pilot RCT will be asked to sign an RCT specific informed consent in addition.

14.2 Ethical and Regulatory Approvals

The protocol, informed consent form, participant information sheet and any proposed advertising material will be submitted to the Ethics Committee of the Medical University of Graz, Austria.

The Investigator will submit and, where necessary, obtain approval from the above parties for all substantial amendments to the original approved documents.

15. FINANCE

This study will be jointly funded by the Institute of Molecular Biosciences, University of Graz and the Division of Endocrinology, Medical University of Graz, Austria.

16. INSURANCE

Participant insurance according to legal requirements will be contracted.

CONFIDENTIAL

